9.1 INCLUSION CRITERIA

Subjects must fulfill all of the following inclusion criteria to be eligible for participation at screening and at Visit 1; Week 0/Day 0:

1. Adult males or females, 18 years of age or older.
2. Demonstrated willingness to participate in the study as documented by signed informed consent.
3. Females of non-childbearing potential defined as postmenopausal (>45 years of age with amenorrhea for at least 12 months or any age with amenorrhea for at least 6 months and a serum follicle stimulating hormone [FSH] level >40 IU/L at Screening); or permanently sterilized (e.g., bilateral tubal occlusion, hysterectomy, bilateral salpingectomy, oophorectomy); or otherwise incapable of pregnancy

OR

Females of child bearing potential (FOCBP) or males who agree to practice two highly effective methods of birth control (as determined by the Investigator; one of the methods must be a barrier technique) from Screening through the end of study participation (Visit 9, Week 16/Day 112).

4. Prior confirmed diagnosis of RCD-II defined by the following criteria: celiac disease confirmed by histology, endoscopy or serology; with persistent and recurrent symptoms (e.g., diarrhea, weight loss, abdominal pain); with abnormal small bowel histology; with aberrant intraepithelial lymphocytosis of > 20% aberrant IELs vs total IELs (as determined by flow cytometry (or >50% if determined by immunohistochemistry); despite adherence to a strict GFD for at least 6 months and after exclusion of other potential causes of symptomatic non-response (e.g., microscopic colitis, bacterial overgrowth, lactose intolerance, exocrine pancreatic insufficiency, hyperthyroidism, etc.) and intestinal histological abnormality (autoimmune enteropathy, giardiasis, immunodeficiency, collagenous sprue, Whipple's disease, etc.).

NOTE: Subjects who have been treated for RCD-II must continue to have increased aberrant IELs (>20% vs total IELs vs total IEL by flow cytometry or >50% by IHC) and abnormal small bowel histology (Marsh \geq 1) and must have had prior history of symptoms; however, symptoms are not required of previously treated subjects, or subjects being treated with steroids, at the time of study entry.

5. Total attempted adherence to a GFD for at least 6 consecutive months prior to screening. Subjects must also agree to make no changes to their current GFD for the duration of study participation.

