at the histology central laboratory. The Central Pathologist, blinded to treatment assignment, will assess villus height (VH, in micrometers) and crypt depth (CD, in micrometers) and their ratio, VH:CD ratio. Further, the Marsh-Oberhuber score will be given (M0, M1, M2, M3a, M3b, or M3c) and the density of CD3-positive IELs (cells/100 epithelial cells) will be assessed. Histology and immunohistochemistry (IHC, e.g., the determination of NKG2D on IEL) analysis will be performed following standard operating procedures for fixed biopsy specimen orientation, paraffin embedding, cutting, staining and scanning for whole slide virtual microscopy. Standard operating procedures will also be followed for biopsy morphometry readings using validated methods (Taavela *et al*, 2013). If it is not feasible to measure at least 3 villus-crypt units for a subject's given biopsies, even after re-cutting, the results will be considered not evaluable.

- iii. Three specimens collected for experimental biomarkers: Approximately three (3) specimens will be used for biomarker research. Two fragments will be placed in mRNA preservative for future mRNA analysis and one will be used for TcR clonality (fresh, frozen or embedded in paraffin).
- iv. Optionally, two fragments for functional experiments: Two specimens, if available, may be used fresh in select sites for analysis of IL-15 related functional biomarkers. Measurement of AMG 714 in the biopsies may be attempted. In Finland one or both optional specimens will be used in some patients for crypt cell "mini-gut" *in vitro* culture at baseline and post-treatment to study biomarkers of epithelial cell differentiation in the crypt-villous axis.

Every effort will be made to collect all 11 to 13 specimens, but should this number not be reached, the specimens will be allocated in the order indicated.

13.3 CLINICAL RESPONSE: BRISTOL STOOL FORM SCALE (BSFS) AND GASTROINTESTINAL SYMPTOMS RATING SCALE (GSRS)

Clinical Response, based on symptoms recorded with patient reported outcome (PRO) questionnaires, will be considered secondary endpoints.

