22.6 SECONDARY ENDPOINTS

Secondary endpoints will be described in the SAP and will include:

- Immunological Response 2: Reduction from baseline in the % of aberrant IELs vs intestinal epithelial cells
- Histological Response: improvement from baseline in small intestinal VH:CD ratio score, Marsh score and total IEL counts
 - VH:CD ratio by validated morphometry. Includes the % of patients with histological remission (VH:CD > 2).
 - Marsh-Oberhuber classes, Marsh 0, 1, 2, 3a-c. Grouping by converting the morphometric results into Marsh classes (Mäki-Jilab converter). Includes the % of patients with histological remission (Marsh 0-1).
 - IEL: for mucosal inflammation the density of IELs/100 epithelial cells will be calculated. The analysis will also include the percentage of patients with normalization of IEL counts vs. epithelial cells (% IELs < 50%).

- Clinical response: change from baseline in symptoms,
 - BSFS and number bowel movements by day and week
 - GSRS and CeD-GSRS, by week

In general, efficacy measures which require pre- and post-treatment biopsies will be based on the PP population (at least 2 biopsies, the second at least on Week 6 or later). Continuous variables will be analyzed based on the ITT population.

Change from baseline of Immunological Response 2, VH:CD and of total IEL counts will be analyzed using the same method as for the primary endpoint.

The Marsh scores will be analyzed using a multinomial logistic regression model, where treatment group, baseline Marsh score, and a treatment group-by-baseline Marsh score interaction term will be included in the model.

The secondary variable BSFS will be analyzed by calculating daily and weekly number and type of bowel movements. The bowel movement counts will be analyzed using generalized linear mixed models with subject as random effect. The statistical model will also include treatment group, time (week) and their interaction. The change in the weekly BSFS scores will mainly be assessed with descriptive statistics, where change from the 'normal (mid-scale)' will be explored. The GSRS and the CeD-GSRS will be analyzed using a linear mixed effects repeated measures model (MMRM) with the baseline value, treatment group, time point and a time point-by-treatment group interaction term as fixed effects with an underlying correlation structure between the time points that results in the best fit for the model. Subject will be included as a random effect.

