As a secondary assessment, the same model will be fitted using the absolute change in VH:CD as a response variable. The modelling results (ANOVA table, parameter estimates, estimated treatment effect, marginal (i.e. least squares) means estimates and results of the check of assumptions) will be tabulated and 95% confidence intervals added, where appropriate.

The baseline and post-baseline values along with the change from baseline values (both relative and absolute) will also be described by summary statistics and tabulated by treatment group. Baseline and post baseline values will also be listed.

The analysis will also include a frequency table by treatment group to summarize the percentage of patients with at least 30% improvement from baseline in VH:CD based on the second biopsy after Week 6.

PP population will be used for the analysis.

Histological Response: Change from baseline in Marsh score

Marsh-Oberhuber classification (Marsh, 1992; Oberhuber, 2000) i.e. the Marsh score, a commonly used histological score with possible values 0, 1, 2, 3a, 3b, 3c with 0 being the best and 3c the worst, will be assessed at screening and Week 12 biopsies.

The Marsh scores will be analysed using a simple logistic regression model, where improvement from baseline in the Marsh score is used as dependent variable and treatment group will be included in the model as explanatory variable. For modelling purposes, a binary variable with values 1 (in case improvement in Marsh scores, i.e. any decrease in score from baseline to Week 12, was observed) and 0 (no improvement in Marsh scores) will be used as a response. Logit function will be used as the link function. The following model will be fitted:

$$\log\left(\frac{p_j}{1-p_j}\right) = \mu + \alpha_j,$$

where

$Y_j \sim \text{Bin}(p_j, n_j)$ – is the number of subjects with improvement in Marsh scores by Week 12 in treatment group j ($j = 1, 2$),

p_j is the probability of improvement in Marsh score for subjects in treatment group j by Week 12,

μ is the overall mean (on logit scale),

α_j is the fixed effect due to treatment j on the logit scale.

The odds ratio for AMG 714 vs placebo groups will be reported and the following formula will be used for obtaining the ratio:

$$OR = \exp(\alpha_{AMG\ 714} - \alpha_{placebo}),$$

where $\alpha_{AMG\ 714}$ denotes the treatment effect of AMG 714 on logit scale and $\alpha_{placebo}$ denotes the placebo effect on logit scale.

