The following SAS code will be used to fit the above-specified model:

```
proc genmod data=marsh descending;
  class trt;
  model marsh_imp = trt / dist=bin link=logit lrci type3;
  estimate 'OR AMG vs PLA ' trt 1 -1 / exp ;
  lsmeans trt /cl ilink;
  ods output ParameterEstimates=Par_est Estimates=Eff_est
             Type3=Type3
             LSMeans=Ls_mean;
run;
```

The modelling results (parameter estimates, estimated odds ratio of AMG 714 vs placebo, marginal (i.e. least squares) means estimates for treatment groups) will be tabulated and 95% confidence intervals added, where appropriate. Odds ratio and marginal means estimates for the probabilities will be presented on the original (probability) scale.

The baseline and post-baseline frequencies of all categories of the Marsh score scale, along with change from baseline frequencies will be tabulated by treatment group. Baseline and post baseline values will also be listed.

The analysis will also include the percentage of subjects with complete remission of the histological abnormalities according to the Marsh score, i.e., the % of subjects with Marsh scores 0-1. Frequency table by treatment group will be used for summarizing these results.

PP population will be used for the analysis.

Histological Response: Relative (%) change from baseline in total IEL counts

Change from baseline in total IEL counts (i.e., density of IELs by IHC) will be analysed using the same method as for the primary endpoint, i.e. the following model will be fitted:

$$Y_{ij} = \mu + \beta \cdot \text{baseline IEL}_{ij} + \alpha_j + \varepsilon_{ij},$$

where

Y_{ij} is the relative (%) reduction from baseline in the total IEL counts for subject i ($i = 1, \dots, n_j$) from treatment group j ($j = 1, 2$),

μ is the overall mean,

β is the parameter estimate of baseline total IEL count,

α_j is the fixed effect due to treatment j ,

ε_{ij} is the random error for subject i from treatment group j ; $\varepsilon_{ij} \sim N(0, \sigma_\varepsilon^2)$.

The following SAS code will be used to fit the above-specified model:

```
proc glm data=IELc alpha=0.05 outstat=F_tests;
  class trt;
  model IELc_change = bl_IELc trt / clparm solution SS1 SS2;
  estimate "AMG 714 vs Placebo" trt 1 -1;
```

```
lsmeans trt /cl stderr;  
ods output ParameterEstimates=Par_est LSMeanCL=LS_meanCL  
LSMeans=LS_mean OverallANOVA=ANOVA Estimates=Eff_est;  
run;
```

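### Protocol and SAP specify different Marsh analyses: the protocol's model is too large for 24 subjects, and the SAP's yes/no model has an inexact test and often no finite odds ratio

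*SAP*

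**What the plan says.** Protocol 22.6, repeated in the synopsis, prescribes a "multinomial logistic regression model, where treatment group, baseline Marsh score, and a treatment group-by-baseline Marsh score interaction term". Protocol 13.2 defines the outcome: "Further, the Marsh-Oberhuber score will be given (M0, M1, M2, M3a, M3b, or M3c", which is six ordered classes.

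SAP 8.6.2 prescribes something else: "The Marsh scores will be analysed using a simple logistic regression model, where improvement from baseline in the Marsh score" is the dependent variable and treatment group the explanatory variable. The response is 1 if "any decrease in score from baseline to Week 12, was observed) and 0 (no improvement in Marsh scores"). The code confirms that there is no baseline term: "model marsh_imp = trt / dist=bin link=logit lrci type3".

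The analysis uses the per-protocol population. SAP 8.2 sets the level for all hypotheses other than the primary one at 0.05, two-sided. SAP 8.6.2 also tabulates every Marsh category at baseline and after baseline, the changes from baseline, and the percentage with Marsh 0 or 1.

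**The concern.** Marsh score is a named secondary histology endpoint, and the two current documents give it two incompatible inferential analyses. They differ in response, covariates and type of model.

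The protocol model is very large for the planned sample. The SAP model is small enough, but with 8 placebo subjects a zero count is likely, and large-sample logistic tests and odds ratios behave badly there. It counts 3c to 3b the same as 3c to 0, and counts unchanged subjects the same as worsened ones.

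At stake is whether the reported Marsh p-value and odds ratio can be taken at face value, and whether it is settled in advance which analysis produces them.

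**Working it through.** **Sample size.** The documents give no power for Marsh. The 24 subjects come from the primary endpoint (Protocol 22.1, SAP 7): difference 20 points, SD 17.4, two-sided alpha 0.10, 2:1 allocation. The noncentrality is (20/17.4) × √(16×8/24) = 2.65 on 22 degrees of freedom, giving 82.3% power. This agrees with the stated figure of at least about 80%. The Marsh analysis inherits 16 versus 8 at most.

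**Protocol model, number of coefficients.** Six classes give 5 nominal logits. Each logit has an intercept, a treatment term, baseline terms and interaction terms.
- Baseline as a linear score: 5 × (1+1+1+1) = 20.
- Baseline as five classes: 5 × (1+1+4+4) = 50. Five classes applies if nobody enters at Marsh 0. Protocol 9.1 requires "abnormal small bowel histology (Marsh" grade 1 or higher) of previously treated subjects.
- Baseline as six classes: 5 × (1+1+5+5) = 60.

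Trials of 16 versus 8 were simulated under assumed Marsh distributions, because the documents give none. Finite maximum-likelihood estimates were absent in 99 to 100% of trials with six classes, whether baseline was linear or categorical. Grouping to four or three classes still gave 96 to 100%. A control run with 2,400 subjects showed no such failure.

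**SAP model, type I error.** All outcomes x of 16 and y of 8 were enumerated with binomial weights. The likelihood-ratio statistic is G = 2[l(x,16) + l(y,8) − l(x+y,24)], where l(x,n) = x ln(x/n) + (n−x) ln(1−x/n), referred to chi-square with 1 degree of freedom at 0.05.

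| Common improvement rate | Likelihood ratio | Fisher |
|---|---|---|
| 10% | 4.5% | 0.9% |
| 20% | 7.0% | 1.6% |
| 25% | 7.4% | 1.8% |
| 30% | 7.2% | 2.0% |

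As an example, take 5/16 versus 0/8. G = 2[−9.937 + 0 + 12.282] = 4.69, so p = 0.030. Fisher's p is (4368+1120+56)/42504 = 0.130. The odds ratio is infinite.

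**SAP model, odds ratio.** With 50% improving on active, an all-or-none arm is almost always a placebo arm with 0/8:
- placebo rate 5%: 0.95⁸ = 66%
- placebo rate 10%: 0.90⁸ = 43%
- placebo rate 20%: 0.80⁸ = 17%

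**Which test governs.** The SAP code requests both a Type 3 test (likelihood ratio by default) and an estimated odds ratio (Wald). The text does not say which p-value counts. The choice matters:

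| Active vs placebo improving | Likelihood ratio | Wald | Fisher |
|---|---|---|---|
| 50% vs 10% | 58% | 9% | 35% |
| 50% vs 20% | 33% | 9% | 19% |

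**Yes/no test against a rank test.** The order depends on the assumed changes. In three scenarios where active subjects also worsen less often than placebo subjects, power was 43, 33 and 49% for the likelihood-ratio test, against 45–47, 41 and 60% for Wilcoxon on grade change. In two scenarios with equal worsening it was 57–59% and 52%, against 32–36% and 25–26%.

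**The case against.** - **The SAP governs.** Protocol 22 leaves detailed methodology to the SAP, and 22.6 says the secondary endpoints will be described there. The SAP gives an equation, a coding and a program, so the operative analysis can be identified. This stands and limits the consequence of the conflict. It does not remove a different model from the protocol, or repair the SAP's test.
- **Multinomial may not mean nominal logits on six classes.** Protocol 22.6 mentions grouping. With four groups and a linear baseline the count is 3 × 4 = 12. A cumulative-logit model on six classes with a linear baseline has 5 + 3 = 8 parameters and was separated in only 1 to 19% of simulated trials. So a flat statement that no version can be fitted would be too strong. The protocol does not state a cumulative link, however, and the nominal grouped versions still failed.
- **A reader might infer that the SAP analysis ignores baseline, size of change and worsening.** The documents do not support that. Baseline defines the response, and the SAP tabulates all categories and changes. VH:CD has its own baseline-adjusted analysis. What is missing is a baseline covariate, and any use of size or worsening, in the Marsh test itself.
- **A reader might infer that the SAP test is less powerful than a rank test.** The documents give no Marsh distribution, and the order reverses when worsening is equal between arms.
- **The endpoint is secondary in an exploratory study.** The go/no-go rule in Protocol 13.1 rests on the two Immunological Responses. This stands.

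**Conclusion.** The point holds in a limited form. The two documents conflict on the Marsh analysis. The protocol's model, in its ordinary nominal reading, asks for 20 to 60 coefficients from at most 24 subjects and cannot be reliably fitted.

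The SAP's model can usually be fitted. Its likelihood-ratio test runs at about 7% instead of 5% for common improvement rates of 20 to 30%, though not at 10%. Its odds ratio has no finite estimate in about 17 to 66% of trials under the rates considered.

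The coefficient counts and the binomial enumeration follow from the planned 16 versus 8. The improvement rates and the Marsh distributions behind the separation figures are assumptions. Losses from the per-protocol population would reduce the numbers further. No claim is made that ranks give more power, and the primary conclusion is not affected.

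**What to change.** Replace the multinomial model in the Protocol synopsis and 22.6, and state the same single analysis in SAP 8.6.2, labelled as secondary. Either option would do:
- a permutation Wilcoxon test on change in ordered grade, or a rank ANCOVA with baseline grade tested by permutation; or
- if any decrease remains the outcome, an exact test with an exact or Firth interval for the odds ratio.

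Say which p-value is reported. Keep the category and change tables as descriptive output.

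The cost is wording in two documents; no new data are needed. There are downsides. An exact test on the yes/no outcome is conservative and will give a less favourable p-value than the likelihood-ratio test (0.130 against 0.030 in the example). A rank test on grade change needs a stated numerical coding of 0, 1, 2, 3a, 3b and 3c, for instance 0 to 5, which treats the steps as equally spaced.
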